(Aim 1) Examine the effect of lorcaserin compared to placebo, on reductions in cannabis use among treatment-seeking outpatients with CUD, **with the primary outcome measured by average weekly mean episodes of any cannabis use (including edibles, vaping, and other variable potency cannabinoid products) per day.**

(Aim 2) Examine the effect of lorcaserin compared to placebo on behavioral and self-report measures of impulsivity among individuals with CUD during the medication lead-in phase (weeks 2-3).

Secondary Aim: If the hypotheses of the Primary Aims are supported, we will examine whether reductions in impulsivity (during weeks 2-3) mediates the effect of lorcaserin on cannabis use (during weeks 8-13).

Exploratory Aims: To explore the effect of lorcaserin compared to placebo on (1) drop-out rates, (2) time to discontinuation from study, (3) treatment adherence, and (4) nicotine use.

Description of Subject Population

Sample #1

Specify subject population

Adults with cannabis use disorder

Number of completers required to accomplish study aims

60

Projected number of subjects who will be enrolled to obtain required number of completers

90

Age range of subject population

18-70

Gender, Racial and Ethnic Breakdown

The study described in the present application seeks to include women and minorities; the study does not exclude any potential participants on the basis of race and gender. Based on previous studies conducted at STARS, the sample is expected to include approximately 50% Caucasian, 22% Hispanic, 24% African-American, 4% other racial groups. Approximately 30% will be women. This profile is representative of the areas from which our treatment program draws patients in New York City and the greater metropolitan area.

Description of subject population

We plan to enroll 90 participants into the study who meet criteria for current CUD and all other study criteria.

Recruitment Procedures

Describe settings where recruitment will occur

The location consists of one site: the Substance Treatment and Research Services (STARS) satellite location (STARS Downtown) situated at [name]. STARS Downtown is leased by NY Presbyterian Hospital Department of Psychiatry.

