Standard Assessments (Weeks 1-13): The following will be completed at every study visit: vital signs, BMI, and TLFB for cannabis use (primary outcome measure). Once per week, participants will provide a urine sample tested for THC-COOH levels and have a study physician evaluation assessing participant's medical and psychiatric status, **in addition to use of substances other than cannabis, and will** include Clinical Global Impressions (CGI) scales for patients' overall well-being and cannabis use. **If a CGI of 6 or more is noted, the study physician and staff will review with participants at his/her next visit to the clinic.** Participants who clinically worsen as measured with $CGI \geq 6$ for 2 consecutive weeks will be

further evaluated by a clinician and case reviewed at the clinic lab meeting as to whether discontinuation from the study is appropriate. If it is clinically determined the participant should be discontinued, he/she will be given referrals for treatment.

Baseline Assessments (Week 1): Prior to randomization and start of study medication, participants will complete baseline assessments in addition to screening and the standard assessments described above. These include EMA prompted through their phone regarding their cannabis, tobacco, other substance use and self-report of impulsivity, study visit assessments including impulsivity measure battery and Fagerstrom Test for Nicotine Dependence (FTND).

Randomization: Participants will be randomly allocated (1:1) to receive lorcaserin or placebo and stratified by the severity of cannabis use at baseline. Severity of use will be categorized as "high" versus "low" users. High users will be defined as those who use 5 or more days per week, averaged per week over the course of the last 1 month. Low users will be defined as those who use less than 5 days per week, averaged per week over the course of the last 1 month. This study will inform future research on stratification for impulsivity.

Medication Dosing Schedule (Weeks 2-13): Participants will begin medication on Day 8 of week 2.

Participants will take 1 dose of lorcaserin 10mg on Day 8. On Day 9, participants will take lorcaserin XR 20mg per day and continue this dose for the remainder of the treatment trial if tolerated. Flexible, reduced dosing is available for participants with immediate release lorcaserin.

The medication lead-in phase occurs during weeks 2-3.

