During this time, participants will also complete daily EMA regarding cannabis use, other substance use including nicotine, and self-report of impulsivity in addition to study-visit assessments. Participants will be instructed to have a target reduce use or quit day, consistent with the participant's treatments goals, by Day 22 of the trial (start of week 4) though are encouraged to attempt to achieve reductions in cannabis use throughout the study and following any relapses. On the first day of week 13, participants will take 1 dose of lorcaserin 10mg before discontinuation.

Study Procedures (Weeks 2-13): Medication Adherence Measurement and Study Procedure

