phones at 9:30pm but can be completed at any time when activities are done for the day. Responses are uploaded in real-time to a secure Illumiv server. (3b) At Study Visits: UPPS-P Impulsive Behavior Scale¹⁰⁴- 59 item questionnaire assesses 5 facets of impulsivity including sensation seeking, lack of premeditation, lack of perseverance, negative urgency, and positive urgency. Adverse Effects Measures: The Systematic Assessment for Treatment and Emergent Events (SAFTEE) will be performed weekly by the study physician to identify adverse symptoms.

Mood and Suicide Measures: Hamilton Depression Scale (HAM-D): We use a 25-item, structured interview version that incorporates the reverse vegetative symptoms of atypical depression but permits calculation of the standard 17 and 21 item scores that are imbedded in the scale. Completed at baseline, weeks 4, 9, and 13. Columbia Suicide Severity Rating Scale (C-SSRS) This is a comprehensive assessment that identifies whether someone is at risk for suicide, assesses the severity and immediacy of that risk, and gauges the level of support that the person needs. Completed at baseline, weeks 4, 9, and 13. Exploratory Assessments:

Participant drop-out and time to drop-out will be assessed. Fagerstrom Test for Nicotine Dependence (FTND) This 6 item self-report questionnaire assesses severity of nicotine dependence and is completed at weeks 1 and 13. Treatment Adherence will be assessed by medication adherence (see above), % response to EMA, and visits attended. Following completion of the study, participants interested in continuing treatment will be given community referrals and bridged by the study physician until first available appointment.

Medication Management: The participants will receive weekly medication management as adjunct psychosocial support with the psychiatrist. During this visit each week, the psychiatrist will monitor for medication effects in addition to providing counseling aimed at adherence with study medication, compliance with study procedures, promoting goals toward abstinence or reduced use of cannabis, promotion of positive health behaviors, and encouraging engagement in other supports outside of the study (eg: mutual support meetings, relationships with family, friends).

You can upload charts or diagrams if any
Table 1_IRB_2018.pdf

Criteria for Early Discontinuation

Criteria for Early Discontinuation

Drop out criteria during the screening and study period include:

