Please create or insert a table describing the proposed collection of blood or other biological specimens. Blood samples (20ml) for routine analyses (ie: chemistry and hematology) will be taken at the time of medical screening. They will be repeated at 1 month following initiation of study medication and then end of study. Women will receive a serum pregnancy test at screening, followed by urine pregnancy testing every month throughout the study following initiation of medication. Quantitative urine toxicology will be collected at screening, followed by quantitative urine THC levels and creatinine twice weekly throughout the study.

Blood and Other Biological Sample(s)	Time Point(s) Collected
Blood chemistries, CBC, liver function tests	Screening, week 13
Serum pregnancy test	Screening
Urinalysis	Screening
Urine pregnancy test	Screening, week 2, 4, 9, 13
Quantitative urine toxicology and creatinine	Screening
Quantitative urine delta-9-THC and creatinine	Weekly following start of study

Assessment Instruments

Create a table or give a brief description of the instruments that will be used for assessment

Medical/Physiological Measurements

Vital Signs and Weight-5min

History and Physical Examination-30min

Electrocardiogram-15min

Pregnancy Test urine—5min

Pregnancy Test serum-5min

Urinalysis-5min

Urine testing for delta-9-THC and cannabinoids (At Screening)-5min

Quantitative urine toxicology with creatinine (weekly throughout study)-5min

Serum Laboratory Examination (CBC, Chem-7, LFTs)-5min

Interviews

Clinical Global Impressions Scale Observer (CGI-O)-5min

Timeline Follow-Back (TLFB)-10min

Hamilton Depression Scale (HAM-D)-5min

Systematic Assessment for Treatment Emergent Effects (SAFTEE)-3min

Columbia-Suicide Severity Rating Scale (C-SSRS)- 5min

Self-Reports

Fagerstrom Test for Nicotine Dependence (FTND)-5min

EMA self reporting on substance use and BIS-7-3min

-participants can self-initiate use of cannabis (log episodes of use) at any time of day through the EMA application

-Daily throughout the study, participants will receive a prompt in the evening asking about number of episodes of use of cannabis, number of cigarettes, and report of any of other substance use.

-During weeks 1, 2, 3, 4, and 13, participants will be asked to complete daily BIS-7 self-reports. The BIS (Barratt Impulsiveness Scale)-7 is an abbreviated version of the BIS-30. (Ansell, 2015)

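### The safety blood schedule contradicts itself: the text has a draw one month into treatment, the table directly below it does not

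*Protocol*

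**What the plan says.** The main conflict lies within one section of the protocol, Blood and other Biological Samples.

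- **Text:** 20 ml is drawn for routine chemistry and hematology at medical screening. Of these samples it then says: "They will be repeated at 1 month following initiation of study medication and then end of study".
- **Table below the text:** the row "Blood chemistries, CBC, liver function tests" has two time points, screening and week 13. The urine pregnancy row of the same table reads "Screening, week 2, 4, 9, 13".

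The treatment calendar is in Study Procedures, under Medication Dosing Schedule: "Participants will begin medication on Day 8 of week 2", and "On the first day of week 13, participants will take 1 dose of lorcaserin 10mg before discontinuation". Description of Subject Population gives 60 as the "Number of completers required to accomplish study aims" and states: "We plan to enroll 90 participants into the study who meet criteria for current CUD and all other study criteria".

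On-study urine is described in four places:

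| Place | Frequency | On-study analyte |
|---|---|---|
| Study Procedures, Standard Assessments | once per week | THC-COOH |
| Biological samples, text | twice weekly | THC with creatinine |
| Biological samples, table | weekly | delta-9-THC with creatinine |
| Assessment Instruments list | weekly | quantitative toxicology with creatinine |

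**The concern.** The line that staff follow decides whether any chemistry, blood count or liver test is scheduled between the first dose and week 13. The protocol itself treats these values as relevant: exclusion criterion 9 bars raised AST and ALT or impaired renal function at entry.

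If the table is followed, a test that the text schedules is not done. If the text is followed, participants give a sample that the table does not list. Dropout sharpens the point, since a third of those enrolled are not expected to complete. Under the table, anyone who leaves before week 13 contributes no scheduled laboratory value after baseline, so the laboratory safety data would come from completers only.

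The urine discrepancy matters less. It settles how many samples are collected and which assay is requested, but the primary outcome is the Timeline Followback and no stated aim names a urine measure.

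**Working it through.** The protocol gives no figure to reproduce here. The check sets the two schedules on the trial calendar and counts.

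**Calendar.** Study Procedures places the start of week 4 on Day 22, so week *n* starts on Day 7(*n* − 1) + 1.
- Week 2 starts on Day 8, the first dose.
- Week 6 is Day 36 to 42.
- Week 13 is Day 85 to 91. The last scheduled dose is on its first day, Day 85.

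**The one-month draw (text).** Taking a month as 28 to 31 days after the first dose: 8 + 28 = Day 36 to 8 + 31 = Day 39, inside week 6.

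**The week 13 draw.** 85 − 8 = 77 to 91 − 8 = 83 days after the first dose. This is on or after the last dosing day.

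**Interval between the two.** 85 − 39 = 46 to 91 − 36 = 55 days.

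**Draws per participant completing the study**

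| | Text | Table |
|---|---|---|
| Screening | yes | yes |
| One month after starting medication | yes | not listed |
| End of study / week 13 | yes | yes |
| Total | 3 | 2 |
| Volume, if each draw is 20 ml | 60 ml | 40 ml |

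**Trial level**, taking the projection of 60 completers from 90 enrolled:
- Non-completers: 90 − 60 = 30, and 30/90 = 33%. If all leave before week 13, up to 30 have no scheduled draw after baseline under the table.
- The protocol does not say when they leave, so between 0 and 30 of them would reach week 6. The number of one-month draws that depend on the choice is therefore 60 + 0 = 60 to 60 + 30 = 90.

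**Could the table's format explain the omission?** No. Its pregnancy-test row lists weeks 2, 4 and 9 as well as screening and week 13, so the table does carry mid-study time points.

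**Urine.** Over 13 weeks: 13 × 1 = 13 samples (three places) against 13 × 2 = 26 (one place). The visit payments do not settle this: $130 at $5 per visit is 26 visits, two a week, which accommodates either frequency. On analyte, the sample table puts toxicology at screening and delta-9-THC on study, while the instrument list puts delta-9-THC at screening and toxicology weekly.

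**The case against.** The strongest counter-argument is that little follows from the conflict. No criterion for early discontinuation cites a laboratory value. Weekly physician review, vital signs and weight continue under either reading, and the adverse-event interview is weekly too ("SAFTEE) will be performed weekly by the study physician to identify adverse symptoms"). An uploaded Table 1 is not shown and may hold the schedule that staff actually use. This limits the consequence to laboratory monitoring, but does not remove the conflict: Table 1 could agree with at most one of the two lines.

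Several narrower points stand as qualifications:
- The trial-level figures are bounds. They count all 90 enrolled as dosed, yet a baseline week precedes randomization and 2 of 9 pilot enrollees left after consent without receiving medication. For anyone never dosed, a missing later draw is no drug-safety gap, and the text would give no one-month draw either.
- End of study is not defined. If it also means a participant's own early exit, the text would cover early leavers before week 6 as well. The one-month conflict is the same on that reading.
- The text names chemistry and hematology, not liver tests. That liver tests belong to the one-month panel is an inference, supported by the exclusion criteria, which ascertain AST and ALT from the chemistry panel.
- The analyte differences may be loose naming plus two transposed labels in the instrument list, not three intended assays. The frequency conflict is plain.

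**Conclusion.** The concern holds. The text and table of the same section give incompatible schedules for the same blood panel, and nothing else in the protocol resolves it.

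The firm size is three draws against two, the disputed one in week 6. Without it, no scheduled laboratory test falls between the first dose and week 13, leaving 77 to 83 days from the first dose to the first result. The upper bound of 30 of 90 participants (33%) without a scheduled draw after baseline under the table, and the range of 60 to 90 affected draws, rest on the protocol's own completion projection, on all non-completers leaving before week 13, and on all enrolled participants starting medication. They should be read as limits.

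The urine inconsistency also holds but is secondary: 13 against 26 samples per participant, with the on-study analyte not named consistently. No efficacy aim, sample size or primary analysis depends on either point. The blood schedule should be corrected because it changes what is done to participants and what laboratory safety data the trial will have.

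**What to change.** Reconcile the passages. The text and table of Blood and other Biological Samples should carry one identical blood schedule that settles whether the one-month draw takes place, and should say whether end of study means week 13 only or also early exit. Study Procedures, the biological samples text and table, and the Assessment Instruments list should carry one urine frequency and one named on-study analyte, with the screening and on-study labels in the same order. Which version applies is for the protocol team to decide.

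The cost is wording in those places, since every option is already described in one of them. The uploaded Table 1 and consent form, which are not shown, should be checked for agreement and aligned if they differ.

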[name]

Drug #2

Name of the drug

Lorcaserin XR

Manufacturer and other information

Lorcaserin XR (BelviqXR)

Manufacturer and other information

Lorcaserin XR (Belviq XR) is a weight-loss drug developed by Arena Pharmaceuticals. It has serotonergic properties and acts as an anorexiant.

An example of study medication label will appear as follows:

Protocol #

Participant ID: 001-ABC

Study Week: #3

Lorcaserin XR 20mg tablet

Directions for use: Take 1 tablet by mouth daily.

Dispense: 7 tablets

Caution: New Drug-- Limited by Federal (or United States) law to investigational use

Approval Status

IND is approved

IND#

129105

Who holds the IND/IND sponsor?

Other

Enter Name

[name]

Research Related Delay to Treatment

Will research procedures result in a delay to treatment?

No

Treatment to be provided at the end of the study

Upon study completion or at the point of dropout, participants will be provided with referrals to community practitioners and offered the option of continued medical management counseling, focused on goals for abstinence and utilization of additional resources in the community for up to four weeks following the end of the study.

Clinical Treatment Alternatives

Clinical treatment alternatives

Unfortunately, there are no FDA-approved medications for the treatment of cannabis use disorder. Several psychotherapy methods have been shown to be effective in treating cannabis use disorder and include: Relapse Prevention Therapy, a form of CBT; Contingency Management, a prize- or voucher-based incentive treatment; Motivational Enhancement Therapy (MET), a form of Motivational Interviewing; the combination of CBT and MET together; and family therapy. However, success rates for psychotherapies have been modest (less than 50%). During the study, participants are permitted to seek additional help from other providers (therapists and physicians outside of the study). Patients are informed that they may request referral for other treatment options.

Risks/Discomforts/Inconveniences

Risks that could be encountered during the study period

Study Medication Risks: One of the main risks associated with participation is drug administration.

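### No closing bloods, pregnancy test, HAM-D or C-SSRS is named for medicated participants who leave before week 13, and the blood-test text and table disagree

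*Protocol*

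**What the plan says.** **Numbers.** Under Description of Subject Population, the protocol gives 60 for "Number of completers required to accomplish study aims" and 90 for "Projected number of subjects who will be enrolled to obtain required number of completers". It states no dropout rate.

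**Bloods.** Under Blood and other Biological Samples, the text says of the routine blood tests taken at screening: "They will be repeated at 1 month following initiation of study medication and then end of study". The table in the same section lists chemistries, CBC and liver function tests at "Screening, week 13" and nothing between. It places the last urine pregnancy test at week 13, after tests at screening and weeks 2, 4 and 9.

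**Mood and suicidality.** In Study Procedures, the HAM-D and the C-SSRS are each "Completed at baseline, weeks 4, 9, and 13".

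**Assessments not tied to week 13.** In the same section, SAFTEE "will be performed weekly by the study physician to identify adverse symptoms". A physician evaluation with CGI is also weekly, and vital signs and BMI are taken at every visit.

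**Leaving early.** Treatment to be provided at the end of the study deals with dropout: "Upon study completion or at the point of dropout, participants will be provided with referrals to community practitioners". The sentence goes on to offer continued medical management counselling for up to four weeks. Criteria for Early Discontinuation and the procedures for minimizing risks list grounds for stopping or withdrawing a participant and name no closing assessments. One route differs in part: a CGI of 6 or more for two consecutive weeks leads to a documented clinical evaluation that draws on assessments such as the C-SSRS.

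**The concern.** The schedule is written for people who reach week 13, yet the protocol's own numbers imply that a sizeable minority will not. If it is followed as written, a participant who took study drug and then left, or was withdrawn for an adverse effect, has no final bloods, pregnancy test, HAM-D or C-SSRS linked to the exit.

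Two things are at stake. First, the risk section lists depression and suicidal thoughts among the rare but serious effects of the drug. HAM-D and C-SSRS are the scheduled instruments for these, and they are not attached to most exits. Second, end-of-study comparisons of these measures between arms would rest on those who stayed. The protocol makes drop-out rate and time to discontinuation exploratory comparisons between arms, so it allows that retention may differ by treatment. An analysis plan cannot recover an assessment that was never scheduled, so this has to be settled in the protocol.

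**Working it through.** **1. Implied non-completion.** Inputs: 90 enrolled and 60 completers (Description of Subject Population).

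- 90 − 60 = 30, and 30/90 = 33.3%.
- Check: 60/(1 − 1/3) = 90. This shows only that the figures agree with each other, because the third was derived from the same two numbers. An assumed 30% would give 60/0.70 = 85.7, rounded up to 86.

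**2. How many of the 30 would have taken drug.** Week 1 is baseline and medication starts on Day 8, so some of the 30 may leave unexposed. The documents give no figure for the trial.

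- If all 30 leave after starting drug: 30.
- If the pilot pattern held (2 of 3 drop-outs left before any medication): 30 × 1/3 = 10.

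The 10 rests on three people. It is an illustration and not a lower bound.

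**3. What the schedule gives an early leaver.** Day 8 + 30 days = Day 38, which falls in week 6 (Days 36–42). That is about when the one-month draw in the text would occur.

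| Measure | Leaves in week 7 | Leaves at end of week 12 |
|---|---|---|
| Bloods, by the table | screening only | screening only |
| Bloods, by the text (before any end-of-study draw) | about week 6 | about week 6 |
| Urine pregnancy test | week 4 | week 9 |
| HAM-D, C-SSRS as scheduled | week 4 | week 9 |
| SAFTEE, physician review | last weekly assessment attended | last weekly assessment attended |
| Vital signs, BMI | last visit attended | last visit attended |

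A participant who leaves at the end of week 12 (Day 84) has been on study medication from Day 8 to Day 84: 84 − 8 + 1 = 77 days, or 11 weeks. Under the table, that person has no on-treatment blood test. Under the text, there is one, plus another only if the end-of-study draw is taken to apply at an early exit.

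**4. What should not be counted.** The longest interval between scheduled HAM-D and C-SSRS assessments is 9 − 4 = 5 weeks. Every participant has that interval, so it does not measure what dropout costs.

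**5. Exit routes.** The CGI-triggered route has its own evaluation supported by the C-SSRS. The pregnancy route starts from a pregnancy test and the underweight route from a BMI. None of these routes, nor withdrawal for a serious medical condition or for adverse effects, names the full set of bloods, pregnancy test, HAM-D and C-SSRS.

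**The case against.** A reader might infer that early leavers get only referrals and leave with no closing safety data. The protocol does not support that. Counselling is offered alongside the referrals. SAFTEE and physician review are weekly, and vital signs and BMI are taken at each visit, so adverse-event data run to the last attended visit for leavers too. On the CGI route, worsening psychiatric symptoms or substance use lead to a documented evaluation, so a week-7 exit by that route need not rest on a week-4 C-SSRS. These points stand, and they narrow the gap to four measures.

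A reader might also infer that the safety comparison as a whole is biased towards lorcaserin. That goes too far. The adverse-event instrument is collected throughout, so selection could affect only end-of-study comparisons of bloods, pregnancy tests, HAM-D and C-SSRS. If people on drug leave because they tolerate it poorly, those comparisons would look too favourable. That direction is plausible but unproven.

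Two further points have weight. The blood-test text says end of study, which could mean each participant's own end, and the dropout paragraph uses similar wording for leavers and completers alike. The table, however, says week 13, so the ambiguity is itself part of the problem. Also, Study Procedures refers to an uploaded chart (Table 1) that is not shown and may contain an early-termination visit. The absence is therefore established only for the text at hand.

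Finally, two of the three pilot drop-outs left without follow-up, and an exit-visit rule would not reach people who leave that way. This limits how much the fix can recover. It does not justify leaving the rule out for those who are withdrawn by staff or who announce that they are leaving.

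**Conclusion.** The point holds in this limited form. The text shown sets the last HAM-D and C-SSRS and, in the table, the last bloods and urine pregnancy test at week 13. It names no closing set of these for medicated participants who leave earlier. The enrolment figures imply that 30 of 90 (33.3%) will not complete. The number of these who will have taken drug is unknown: at most 30, and about 10 if a pattern seen in three pilot drop-outs held.

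Separately, the blood-test text and table contradict each other. Under the table, anyone who leaves before week 13 has no on-treatment blood test, even after as much as 11 weeks on drug.

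The conclusion rests on reading the table's week 13 literally and on Table 1 having no early-termination visit. If it has one, what remains is a missing cross-reference and the contradiction over bloods. This is a cheap improvement to safety data collection and does not undermine the trial's efficacy aims.

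**What to change.** 1. Under Blood and other Biological Samples, reconcile the text and the table on when bloods are drawn, and define end of study for a participant who leaves early.
2. In Study Procedures, Criteria for Early Discontinuation, Blood and other Biological Samples, and Treatment to be provided at the end of the study, state that the existing week-13 assessments (bloods, urine pregnancy test, HAM-D, C-SSRS) are collected at week 13 or, for a medicated participant who leaves sooner, at that participant's own last visit. State that SAFTEE and C-SSRS are sought by phone if the person will not attend.
3. If Table 1 already shows an early-termination visit, refer to it from those sections instead.

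The cost is protocol wording. No new instrument is added, and the assessments already planned for week 13 are brought forward. Some leavers will decline or be unreachable, and a few exit visits will take longer. The change concerns data collection only and proposes no dose, stopping or treatment rule.
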